## E. Final Statistical Analysis Plan

The primary analysis will be an intention to treat analysis among randomized patients with confirmed COVID-19. The researchers seek to enroll at least 204 Black or Latino patients in each arm to achieve 90% power to detect a mean difference of 1 DOAH, assuming a type I error rate of 0.05. Given that Black and Latino patients comprise 61% of the COVID Watch sample, this indicates a target minimum sample size of at least 1078 patients with confirmed COVID-19.

As the primary analyses, the researchers will use an intention-to-treat approach. The researchers also performed a per protocol analysis including only those patients who actively participated on their allocated protocol (e.g., responded to at least one text-message check-in). For both analyses, the researchers compared mean DAOH between study groups using two-sample t-tests. Adjustment for covariates via regression was not deemed necessary as all sociodemographic and clinical characteristics were well balanced between arms. The researchers also compared continuous secondary outcomes including mean number of outpatient visits, emergency department encounters, and hospitalizations using t-tests. The researchers compared categorical secondary outcomes using Fisher's Exact test. A prespecified subgroup analysis was completed by comparing outcomes for Black and Hispanic patients to White patients. Exploratory subgroup analyses were conducted for age strata and enrollment context (inpatient, outpatient, and ED). All tests were two-sided and a p-value  $< 0.05$  was considered statistically significant in the primary analyses. In subgroup analyses, to account for multiple testing, Bonferroni corrected p-value cut-offs are provided for the results in the supplementary tables. All analyses were conducted using R statistical software version 3.6.0 (R Foundation for Statistical Computing, Vienna, Austria. URL <https://www.R-project.org/>).

[Below is from original SAP]

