## **F. Summary of Amendments and Clarifications to Statistical Analytic Plan**

There were three modifications to the statistical analytic plan. All modifications were made prior ascertaining outcome.

First, the researchers clarify that Bonferroni was used for corrected p-value cut offs to adjust for multiple comparisons for the race subgroup analyses.

Second, the researchers increased the sample size. The rationale for this change was due to a lower-than-expected COVID positivity rate and SD in Days Alive Out of Hospital (DAOH) based on baseline COVID Watch program data through November 30, 2020.

Plan Version	Amendment or Clarification	Dates
Final	Sample size was increased	12/17/20
	Clarified plan to use Bonferroni corrected p-value cut offs to adjust for multiple comparisons for the race subgroup analyses	11/02/20
Original	The approved IRB protocol was considered the original statistical analysis plan. Approval was granted 10/8/20.	10/08/20

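### Optional gain: Holm's step-down on the subgroup tests would hold the same 0.05 familywise bound as the planned Bonferroni cut-offs and reject at least as much

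*Combined protocol and SAP*

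**What the plan says.** Section E (Final Statistical Analysis Plan) describes a prespecified race subgroup analysis and exploratory analyses by age and by enrollment context. For the subgroup analyses it states that "to account for multiple testing, Bonferroni corrected p-value cut-offs are provided for the results in the supplementary tables". It gives neither the number of tests nor a numerical cut-off.

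Section F records, with the date 11/02/20, that "Bonferroni was used for corrected p-value cut offs to adjust for multiple comparisons for the race subgroup analyses". It also states that the SAP changes were made before outcomes were ascertained. Neither section mentions a step-down procedure.

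The primary analyses are tested at 0.05 without this correction, and "All tests were two-sided". The sample-size statement in section E seeks "at least 204 Black or Latino patients in each arm to achieve 90% power". The target is a 1-day difference in the primary outcome, and the calculation is made "assuming a type I error rate of 0.05". That sizing concerns the treatment effect in Black and Latino patients pooled. The text carried over from the original SAP adds race/ethnicity interaction terms and a separate look at Black patients and at Latino patients.

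**The concern.** Bonferroni compares every p-value in the family with 0.05/m, where m is the number of tests. Holm compares the smallest with 0.05/m, the next with 0.05/(m−1), and so on, stopping at the first failure. Both guarantee a familywise error of at most 0.05 with no assumption about dependence, but Holm's later thresholds are looser.

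The race comparisons matter in this trial: the protocol's hypothesis H2b expects a particular benefit in Black and Latino patients. If more than one race comparison reflects a real effect, Bonferroni can miss a difference that Holm would declare under the same error bound.

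**Working it through.** **Inputs.** From section E: two-sided tests, type I error 0.05, 90% power, 204 Black or Latino patients per arm, a difference of 1 day. Not in the documents and therefore assumed: a familywise level of 0.05 for the subgroup tests, the family size m, the power of each contrast, and the correlation between test statistics.

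**The plan's own figure.** n per arm = 2σ²(z₀.₉₇₅ + z₀.₉₀)²/Δ², with z₀.₉₇₅ + z₀.₉₀ = 1.960 + 1.2816 = 3.2415 and Δ = 1. The SD is not stated. Solving for it gives σ = √(204/2)/3.2415 = 10.10/3.2415 = 3.12 days. So 204 can be back-solved but not independently reproduced. The comparison below needs only the standardised mean 3.2415, which is 90% power at unadjusted 0.05.

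**Holm rejects all that Bonferroni rejects.** If p₍ₖ₎ ≤ 0.05/m, every smaller p-value is also at most 0.05/m, and each Holm threshold 0.05/(m−i+1) is at least 0.05/m. Holm therefore does not stop before k.

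**Holm keeps the bound.** With m₀ true nulls, the first true null in the ordering comes no later than step m−m₀+1, so it faces a threshold of at most 0.05/m₀. For any true null to be rejected, at least one null p-value must be at or below 0.05/m₀, which has probability at most m₀ × 0.05/m₀ = 0.05. Independence is not used.

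**Bonferroni power for the assumed contrast.**
- m = 2: cut-off 0.025, z = 2.2414, power Φ(3.2415 − 2.2414) = 84.1%.
- m = 3: cut-off 0.0167, z = 2.3940, power Φ(3.2415 − 2.3940) = 80.2%.

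**Holm power, m = 2, independent tests.** The contrast is declared if its p ≤ 0.025, or if its p lies between 0.025 and 0.05 and the other p ≤ 0.025. With q the other contrast's power at 0.025, power = 0.8414 + (0.9000 − 0.8414) × q.

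| Other contrast | q | Bonferroni | Holm |
|---|---|---|---|
| null | 0.025 | 84.1% | 84.3% |
| half the effect | 0.267 | 84.1% | 85.7% |
| 0.8 of the effect | 0.638 | 84.1% | 87.9% |
| equal effect | 0.841 | 84.1% | 89.1% |

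The contrast with 0.8 of the effect itself moves from 64% to 72%.

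**Holm power, m = 3, independent tests, by simulation** (400,000 or more replicates per scenario).

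| Other two contrasts | Bonferroni | Holm |
|---|---|---|
| both null | 80% | 80% |
| both half the effect | 80% | 82% |
| 0.8 of the effect, and null | 80% | 83% |
| equal effect, and null | 80% | 83–84% |
| 0.8 and 0.5 of the effect | 80% | 84% |
| both equal | 80% | 88% |

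**Correlation.** At an assumed correlation of 0.5, the equal-effect case gives 88% instead of 89% for m = 2, and 87% instead of 88% for m = 3. For m = 2 with a second contrast at 0.8 of the effect, Holm gives 86.5% instead of 87.9%.

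**Other operating characteristics, m = 2, independent tests.**
- Both null: familywise error is 1 − (1 − 0.025)² = 0.0494 for both methods.
- One real, one null: Bonferroni 0.025; Holm 0.025 + 0.025 × 0.8414 = 0.046.
- Both real: the chance of at least one rejection is 97.5% under either method. Holm adds further findings once one is made; it does not add first findings.

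**The case against.** The strongest reply is that this exchanges one valid method for another in supplementary subgroup tables. Bonferroni is valid and conservative, and the amendment log dates the choice before outcome ascertainment. It gives readers one cut-off for every row, and matching simultaneous confidence intervals are simple, which they are not under Holm. Holm also spends more of the error allowance, as the rise from 0.025 to 0.046 shows. All of this stands, except that the interval argument has little force here because the SAP plans no intervals. It makes the change optional without removing the gain.

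Two stronger readings should be resisted. A reader might infer that Bonferroni cuts the trial's planned 90% power to 84% or 80%. The documents do not support this: the 204 per arm is for the pooled Black or Latino treatment effect at unadjusted 0.05, and nothing places that contrast in the corrected family. Separate Black and Latino evaluations would each be smaller. With an assumed 50% unadjusted power per contrast and m = 2, both real, the move is only from 39% to 43%.

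A reader might also infer that the plan gives up power and gets nothing back. It gets a single printed threshold and lower actual error within the bound.

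Independence is doubtful too. If Black and Hispanic patients are each compared with White patients, the two contrasts share a reference group, which is why the correlated results are shown.

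**Conclusion.** The point holds as an optional improvement in efficiency. On any fixed family, Holm keeps familywise error at or below 0.05 and never rejects less than Bonferroni; that part rests on no assumption about the trial.

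The size is illustrative only. For a contrast assumed to have 90% unadjusted power, the range is 84% to 84–89% for two tests and 80% to 80–88% for three. The gain is about zero if no other contrast is real and about 1 to 2 points if the others are half as large (independent tests). The top of each range is reached only when all are equally large, and correlation of 0.5 trims it. Family size, effect pattern and correlation are all assumptions.

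Which tests form the family matters more than the choice between the two methods. Section E speaks of subgroup analyses generally and section F of race only. Because section F is a log, the difference is not counted here as an error, but either method needs the family named.

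**What to change.** In section E, list the race subgroup tests that form the family, so that its scope agrees with the clarification in section F, and state that Holm-adjusted p-values for that family will be reported and read against 0.05. Record the change as a new dated entry in section F, leaving the 11/02/20 entry as it stands.

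Section E is partly in the past tense and already reports balance between arms, so the subgroup results may be known. If they are, keep the prespecified Bonferroni cut-offs, show the Holm values beside them, and label them as added later.

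The cost is a short edit in section E, one log entry and one standard function call in R, the software that section E names. No extra patients or data are needed. The drawbacks are that no single cut-off serves all rows, simple matching simultaneous intervals are lost should they be wanted, and actual familywise error moves closer to 0.05 without exceeding it.

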### 3. Aims

**3.1 Primary outcome.** The primary outcome measure is the difference in Days Alive and Out of Hospital.

**3.2 Secondary outcomes.** The secondary outcome measure is the difference self-reported anxiety on a single question adapted from the Emotional Distress-Anxiety Short Form 4a scale on day 0, 7, and 14 after enrolment in COVID Watch.

**3.3 Exploratory outcomes.** The researchers will explore several other outcomes of interest. These included differences in: 1) 30-day mortality; 2) incidence and timing of remote monitoring escalations to nursing care and subsequent emergency department referrals; 3) health care utilization including outpatient, emergency department, inpatient, and ICU care; 4) self-perceptions of feeling safe at managing illness; and 5) rates of discordance between dyspnea symptoms and hypoxia as measured on home pulse oximetry.

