COVID Watch (<https://covidwatch.waytohealth.org/>) is powered by UPHS’ NIH-funded research and operational texting platform ([www.waytohealth.org](http://www.waytohealth.org)), integrated with UPHS’ EMR. Since hypoxemia is the primary driver of admission and fatality among COVID-19 patients, the researchers focused the algorithm (Appendix Fig 1-3) on shortness of breath, the closest approximation for concerning hypoxemia. Given the rapid and unpredictable decompensation of COVID-19 patients, patients receive clinical support 24 hours/day, 7 days/week. COVID Watch sends twice-daily, scheduled text messages to assess patients for shortness of breath using an algorithm to determine whether patients need an urgent escalation to a team of dedicated nurses within 1 hour (Appendix Fig 4). These nurses are supported by an on-call team of clinicians who can conduct urgent phone or video assessments. At each level patients’ clinical needs are either managed with self-care advice, prescriptions, or a referral to the ED. The majority of COVID Watch patients (83.7%) have been enrolled by outpatient providers conducting telephone and video visits; 8.7% and 7.6% have been enrolled at ED and inpatient discharge, respectively. The program is available at all six of UPHS’s hospitals and EDs, and all 530 affiliated ambulatory settings using the EMR. Any clinical staff member (e.g., RN, physician, medical assistants) logged on to the EMR is able to enroll patients (Appendix Fig 5). Patients can also trigger the algorithmic assessment independent of the scheduled messages. Patients only receive the intervention if they are agreeable (“opt-in”) and can stop anytime. Patients are scheduled to be in COVID Watch for 14 days, with the option to extend to 21 days if interested. A Spanish-language version of COVID Watch was made available to patients on May 18, 2020, with nurses using translation lines to communicate with patients.

COVID Watch engagement is high. To date, nearly 80% of enrolled patients have engaged with the program, defined as responding to scheduled text messages at least once every two days. RNs have managed over 600 calls with a mean response time (median) of 25 minutes (11 minutes). Of the calls, 37% were asked to continue to monitor at home, 41% were scheduled for an urgent follow-up telemedicine visit, and 9% were sent to the ED for emergent evaluation.

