## 8.2 Procedures

1. Patients are started on COVID Watch as routine care based on confirmed or clinical suspicion for COVID-19 via the integration of the Way To Health (W2H) platform with the electronic health record.
2. Patient receives a text message to proceed in COVID Watch as is current routine care.
3. For this study, W2H auto-generates and sends the study's Research Coordinator (RC) a daily excel report with a list of new COVID Watch enrollees at regular intervals (e.g., every 2 hours). The report includes the randomized arm assignment (COVID Watch or COVID Watch + Pulse Oximetry), along with the patient's phone number.
4. The RC alerts patients randomized to COVID Watch + Pulse Oximetry via phone call and/or text message that there will be a next day pulse ox device delivery and that once received, the patient will start to measure and report their oxygen levels. The RC confirms the patient's mailing address and instructs patients that in the meantime, they should continue to respond to COVID Watch check-ins per standard protocol. The patient is instructed to text or call once they have received the pulse oximetry device. If language preference is Spanish, an interpreter is required on the call.

- i. If the patient cannot be reached by text, the RC calls and if necessary, leaves a voicemail and the patient will still be sent a pulse ox.
- 5. The RC sends a pulse oximetry device via UPS 11am and 5pm. The package will include a pulse oximetry device (with barcode), printed patient instructions in the appropriate language, and prepaid, labeled return envelope to be used at the end of their COVID Watch enrollment
- 6. The RC logs device identifier, date and time of drop off of package for each patient
- 7. The RC tracks device receipt (via both UPS tracking and/or patient self-report) and contacts the patient via text and/or phone call to ensure the patient understands how to use the device. If language preference is Spanish, an interpreter is required on the call.
- 8. The RC changes patient protocol from COVID Watch to COVID Watch + Pulse Oximetry.
- 9. The RC follows up with patients via text and/or phone call in the event that the device is not returned within 2 weeks of being discharged from COVID Watch

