## **9.2 Subject confidentiality**

All participant data will be through COVID Watch or the electronic medical record. There will be no paper records or other forms of data collection. Therefore, subject confidentiality will be maintained through the data protections described above in section 11.1.

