Linear mixed effects models will be used to assess the incremental effect of home pulse oximetry on DAOH relative to COVID Watch alone. Random intercepts will be used to account for clustering by testing site. Randomization will theoretically ensure balance of measured and unmeasured covariates between arms. Factors deemed to be associated with the outcome a priori will be adjusted for to increase efficiency. These include: age, sex, race, ethnicity, insurance, median income of residential ZIP code and ED vs. outpatient enrollment.

The researchers will examine heterogeneity in treatment effects using interaction terms by treatment comparator group and: the following (1) location of enrollment (outpatient vs ED); (2) primary care in the health system (yes or no); (3) insurance (none/Medicaid/Medicare/private); and (4) race/ethnicity, including an evaluation of Black and Latino patients separately. A sensitivity analysis will be performed to compare outcomes to UPHS COVID-19 patients not enrolled in COVID Watch using a propensity score analysis. The researchers will record and report all reasons for dropout and missing data, and account for all patients in reports. Because this research is being conducted in the context of routine care and COVID Watch requires a working cell phone, the researchers anticipate fewer losses to follow-up than is typical.

As secondary analyses, the researchers will repeat the above analyses in the full population of randomized patients now including the population of patients placed into COVID Watch who had suspected COVID-19 but ended up having negative COVID-19 tests.

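### The only secondary outcome, self-reported anxiety, falls to an unadjusted test that ignores the day 0 score and has no plan for missing replies, while coordinator contact differs by arm

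*Combined protocol and SAP*

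**What the plan says.** Section 3.2 of the final protocol makes the secondary outcome the difference in "self-reported anxiety on a single question adapted from the Emotional Distress-Anxiety Short Form 4a scale on day 0, 7, and 14". Section 3.3 lists "self-perceptions of feeling safe at managing illness" as an exploratory outcome, with no instrument or time point. Section 9.2 says "All participant data will be through COVID Watch or the electronic medical record", and nothing describes the medical record as holding either item.

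Section 8.2 has the research coordinator contact device-arm patients by phone or text before delivery. After delivery the coordinator "contacts the patient via text and/or phone call to ensure the patient understands how to use the device". No matching step is listed for controls.

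Section 4 gives the only response figure in the documents: before the trial, "nearly 80% of enrolled patients have engaged with the program, defined as responding to scheduled text messages at least once every two days".

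Part E, the final SAP, uses t-tests for continuous secondary outcomes, giving visit and admission counts as examples, and "compared categorical secondary outcomes using" Fisher's exact test. Neither anxiety nor feeling safe is named. The text retained from the original SAP specifies a covariate-adjusted mixed model, but for DAOH only. On missing data it undertakes to record and report reasons and to account for all patients. It then expects few losses on two grounds: the setting is routine care, and "COVID Watch requires a working cell phone, the researchers anticipate fewer losses to follow-up than is typical".

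**The concern.** A self-reported item exists only if the patient answers, and the documents name no second source. A t-test or Fisher's exact test can use only patients who have a score on the day in question. If the extra coordinator contact changes who answers in one arm, the two sets of responders are no longer comparable, and a difference in who replied could be read as an effect of the device on anxiety. The usual protection, the patient's own day 0 score, is collected, but the stated test does not use it. The cell-phone argument is about being reachable and does not show that patients will answer a survey.

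**Working it through.** **What the engagement figure can and cannot say.** 100% minus nearly 80% leaves just over 20% of pre-trial program patients who replied less often than once every two days. This group includes partial responders, and the figure concerns program check-ins, so it is not a survey non-response rate. Purely for scale, if 20% of 1,078 lacked a survey answer, about 216 would be missing, leaving about 431 per arm. The plan has no power calculation or response assumption for anxiety to reproduce.

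**Simple formula.** Suppose there is no true effect, non-responders differ from responders by d SD in both arms, and fractions m0 (control) and m1 (device) are missing. Then

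- bias = (m0 − m1) × d
- SE = √[1/(n(1 − m0)) + 1/(n(1 − m1))]

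Take n = 1,078/2 = 539 per arm (1:1 allocation assumed), m0 = 0.20, m1 = 0.10 and d = 0.5:

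- bias = 0.10 × 0.5 = 0.05 SD
- SE = √(1/431.2 + 1/485.1) = 0.066
- bias/SE = 0.755
- two-sided type I error = P(Z > 1.96 − 0.755) + P(Z < −1.96 − 0.755) = 11.8%

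Other values at n = 539 and m0 = 0.20:

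| m1 | d | Bias (SD) | Type I error |
|---|---|---|---|
| 0.20 | any | 0 | 5.0% |
| 0.15 | 0.2 / 0.5 / 0.8 | 0.010 / 0.025 / 0.040 | 5.3 / 6.6 / 9.2% |
| 0.10 | 0.2 / 0.5 / 0.8 | 0.020 / 0.050 / 0.080 | 6.1 / 11.8 / 22.7% |

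**Simulation of the two analyses.** Assumptions: standardised anxiety score, correlation 0.6 between day 0 and follow-up, no arm effect, two-sided 0.05, 3,000 runs per setting. Response is logistic in day 0 anxiety, falling by 0.5 or 1.0 log-odds per SD. Arm sizes are 539 and 334; the latter is half of 2 × 204/0.61 = 669, the total implied by the SAP's subgroup size. (The gap between 669 and 1,078 is a separate matter.) A positive bias makes the device arm look more anxious.

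| Response, control / device | Unadjusted: bias (SD) | Unadjusted: type I error | Day 0-adjusted: bias (SD) | Day 0-adjusted: type I error |
|---|---|---|---|---|
| 80 / 80% | about 0 | about 5% | about 0 | about 5% |
| 80 / 90% | 0.03 to 0.05 | 6 to 12% | about 0 | 4 to 6% |
| 70 / 90% | 0.06 to 0.10 | 10 to 30% | about 0 | 5 to 6% |

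**Precision.** Adjusting for a covariate with correlation ρ multiplies the standard error by √(1 − ρ²). With ρ = 0.6 this is √0.64 = 0.80, a reduction of about 20%. The simulated ratio with equal response was 0.80 to 0.82. This gain does not need response to differ by arm.

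**Where day 0 adjustment falls short.** If response depends on anxiety at the time of the survey, then at 80% versus 90% and 539 per arm the unadjusted bias is 0.05 to 0.08 SD and the adjusted bias 0.03 to 0.06 SD. Only about a third is removed.

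**The case against.** The strongest reply is that the size of the problem is all assumption. No response rate by arm, no link between response and anxiety and no correlation appears in the documents. With equal response and equal selection the bias is zero, and at 20% versus 15% missing the type I error is only 5.3 to 9.2%. The p < 0.05 criterion is stated for the primary analyses, so no confirmatory claim on anxiety is shown to be at risk. The SAP also gives routine care as a ground for few losses and commits to accounting for all patients. All of this stands, and it limits how strongly the point can be put.

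A reader might also infer more than the documents support:

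- **That over 20% of patients do not answer texts.** The figure is the share below an engagement threshold and includes people who answer less often.
- **That missing a text means missing the survey.** The documents do not say the anxiety item is sent by text. Section 9.1 mentions a web interface for surveys and manual entry by researchers.
- **That the device arm gets two extra prompts a day.** The saturation request in section 5.1 may sit inside the existing twice-daily check-in. The documented asymmetry is the coordinator contact in section 8.2.
- **That device-arm response will be higher.** Extra tasks could also lower it.
- **That the SAP prescribes a responders-only analysis.** This follows from the named tests and the absence of any missing-data method; it is not stated.

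None of this supplies a method for missing replies or a reason to leave the day 0 score unused.

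**Conclusion.** The point holds in a limited form. The plan's only secondary outcome has no named analysis of its own, and the generic test that reaches it is weaker than one using data already collected. Contact is unequal by arm as the procedures are written, so unequal response is plausible, but its size and direction are unknown. The illustrative type I error of 6 to 12%, against 4 to 6% after adjustment, rests on the assumed 80% versus 90% response, a slope of 0.5 to 1.0 per SD, a correlation of 0.6 and dependence on day 0 anxiety. The precision gain of about 20% rests only on the correlation. The change is worth making but does not decide the trial. It would be wrong to infer that the main result is in doubt, because DAOH does not depend on survey replies.

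**What to change.** In part E of the SAP:

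1. Name anxiety and replace the generic test for it with a repeated-measures model (or an ordinal equivalent) for days 7 and 14, with day 0 as a covariate, in the SAP's intention-to-treat population. First confirm that day 0 is answered before the patient is told of the device; the documents do not give this order.
2. State how and when both survey items are delivered, and do not rely on the cell-phone argument for them.
3. Report response by arm and day for anxiety and for feeling safe.
4. Prespecify one delta-adjusted sensitivity analysis for missing anxiety replies, with shifts that may differ by arm, because day 0 adjustment does not remove bias that depends on current anxiety.

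Multiple imputation is optional. It should not be claimed to remove bias for patients who also lack day 0: in a check of the 80% versus 90% setting where the same patients missed both, a likelihood model equivalent to imputing from day 0 left the bias unchanged (0.024 and 0.050 SD at slopes 0.5 and 1.0). Post-randomisation auxiliaries such as escalations need care, because saturation triggers exist only in the device arm. Scoring hospitalised or dead patients in the worst anxiety category is not needed.

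The cost is SAP wording, some extra analysis and reliance on model assumptions. No new data are required.
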